#### **4.4. End of Study Definition**

The end of the study is defined as the date of the last visit of the last participant in the last substudy.

See [Section 10.11.4.4](#) for the end of Substudy A definition.

See [Section 10.12.4.4](#) for the end of Substudy B definition.

See [Section 10.13.4.4](#) for the end of Substudy C definition.

### **5. STUDY POPULATION**

This study can fulfill its objectives only if appropriate participants are enrolled, including participants across diverse and representative racial and ethnic backgrounds. If a prescreening tool is utilized for study recruitment purposes, it will include collection of information that reflects the enrollment of a diverse participant population including, where permitted under local regulations, age, sex, race, and ethnicity. The following eligibility criteria are designed to select participants for whom participation in the study is considered appropriate. All relevant medical and nonmedical conditions should be taken into consideration when deciding whether a particular participant is suitable for this protocol.

Prospective approval of protocol deviations to recruitment and enrollment criteria, also known as protocol waivers or exemptions, is not permitted.

Note: "Enrolled" means a participant's agreement to participate in a clinical study following completion of the informed consent process and randomization to study intervention.

#### **5.1. Inclusion Criteria**

See [Section 10.11.5.1](#) for the Substudy A inclusion criteria.

See [Section 10.12.5.1](#) for the Substudy B inclusion criteria.

See [Section 10.13.5.1](#) for the Substudy C inclusion criteria.

#### **5.2. Exclusion Criteria**

See [Section 10.11.5.2](#) for the Substudy A exclusion criteria.

See [Section 10.12.5.2](#) for the Substudy B exclusion criteria.

See [Section 10.13.5.2](#) for the Substudy C exclusion criteria.

### 5.3. Lifestyle Considerations

#### 5.3.1. Contraception

The investigator or their designee, in consultation with the participant, will confirm that the participant is utilizing an appropriate method of contraception for the individual participant and their partner(s) from the permitted list of contraception methods (see [Section 10.4.4](#)) and will confirm that the participant has been instructed in its consistent and correct use. The investigator or designee will advise the participant to seek advice about the donation and cryopreservation of germ cells prior to the start of study intervention, if applicable.

At time points indicated in the [SoA](#), the investigator or designee will inform the participant of the need to use acceptable effective contraception consistently and correctly and document the conversation and the participant's affirmation in the participant's chart. Participants need to affirm their consistent and correct use of at least 1 of the selected methods of contraception, considering that their risk for pregnancy may have changed since the last visit.

In addition, the investigator or designee will instruct the participant to call immediately if the selected contraception method is discontinued and document the requirement to use an alternate protocol-specified method, including if the participant will no longer use abstinence as the selected contraception method, or if pregnancy is known or suspected in the participant or partner.

#### 5.4. Screen Failures

Screen failures are defined as participants who consent to participate in the clinical study but are not subsequently randomized in the study. A minimal set of screen failure information is required to ensure transparent reporting of screen failure participants to meet the CONSORT publishing requirements and to respond to queries from regulatory authorities. Minimal information includes demography, screen failure details, and any SAEs.

Individuals who do not meet the criteria for participation in this study (screen failure) may be rescreened under a new participant number.

#### 5.5. Criteria for Temporarily Delaying Enrollment/Randomization/Administration of Study Intervention

See [Section 10.11.5.5](#) for Substudy A temporary delay criteria.

See [Section 10.12.5.5](#) for Substudy B temporary delay criteria.

See [Section 10.13.5.5](#) for Substudy C temporary delay criteria.

### 6. STUDY INTERVENTION(S) AND CONCOMITANT THERAPY

Study interventions are all prespecified investigational, medical devices, and other interventions (eg, surgical and behavioral) intended to be administered to the study participants during the study conduct.

## 6.1. Study Intervention(s) Administered

See [Section 10.11.6.1](#) for study interventions administered during Substudy A.

See [Section 10.12.6.1](#) for study interventions administered during Substudy B.

See [Section 10.13.6.1](#) for study interventions administered during Substudy C.

Table 1 describes the vaccine details for each of the constituent parts of the modRNA-containing study interventions.

**Table 1. Substudy A, Substudy B, and Substudy C: Vaccine Details**

Vaccine Preparation	Influenza Strains	CCI
PF-07966731, Influenza modRNA Suspension for Injection, 0.1 mg/mL	CCI	
PF-07871853, Influenza modRNA Suspension for Injection, 0.1 mg/mL		
PF-08010605, Influenza modRNA Suspension for Injection, 0.1 mg/mL		
PF-07872963, Influenza modRNA Suspension for Injection, 0.1 mg/mL		
PF-07973057, Quadrivalent Influenza modRNA Suspension for Injection, 0.06 mg/mL	2023-2024 northern hemisphere seasonal strains recommended by WHO for CCI influenza vaccines	
PF-07973057, Quadrivalent Influenza modRNA Suspension for Injection, 0.12 mg/mL	2023-2024 northern hemisphere seasonal strains recommended by WHO for CCI influenza vaccines	
PF-08011473, Trivalent Influenza modRNA Suspension for Injection, 0.09 mg/mL (CCI)	2023-2024 northern hemisphere seasonal strains recommended by WHO for CCI influenza vaccines	
PF-07973257, Influenza mod RNA Suspension for Injection, 0.1 mg/mL	CCI	
PF-07872962, Influenza modRNA Suspension for Injection, 0.1 mg/mL		
PF-07872964, Influenza modRNA Suspension for Injection, 0.1 mg/mL		

### 6.1.1. Administration

See [Section 10.11.6.1.1](#) for study intervention administration details for Substudy A.

See [Section 10.12.6.1.1](#) for study intervention administration details for Substudy B.

See [Section 10.13.6.1.1](#) for study intervention administration details for Substudy C.

Standard vaccination practices must be observed and vaccine must not be injected into blood vessels. Appropriate medication and other supportive measures for management of an acute hypersensitivity reaction must be available in accordance with local guidelines for standard immunization practices.

Administration of study interventions will be performed by an appropriately qualified, trained, and vaccine-experienced member of the study staff (eg, physician, nurse, physician's assistant, nurse practitioner, pharmacist, or medical assistant) as allowed by local, state, and institutional guidance.

Study intervention administration details will be recorded on the CRF.

### 6.1.2. Medical Devices

Comparator vaccines detailed in [Section 10.11.6.1](#), [Section 10.12.6.1](#), and [Section 10.13.6.1](#) may be provided as a PFS and, in which case, should be considered a medical device.

1. Instructions for medical device use are provided in the USPI.
2. All medical device deficiencies (including malfunction, use error, and inadequate labeling) for the above-listed medical devices shall be documented and reported by the investigator throughout the clinical investigation (see [Section 8.4.9](#)) and appropriately managed by the sponsor.

### 6.2. Preparation, Handling, Storage, and Accountability

1. The investigator or designee must confirm that appropriate conditions (eg, temperature) have been maintained during transit for all study interventions received and any discrepancies are reported and resolved before use of the study intervention.
2. Only participants enrolled in the study may receive study intervention and only authorized site staff may supply, prepare, and/or administer study intervention.
3. All study interventions must be stored in a secure, environmentally controlled, and monitored (manual or automated recording) area in accordance with the labeled storage conditions with access limited to the investigator and authorized site staff. At a minimum, daily minimum and maximum temperatures for all site storage locations must be documented and available upon request. Data for nonworking days must indicate the minimum and maximum temperatures since previously documented upon return to business.

4. Any excursions from the study intervention label storage conditions should be reported to Pfizer upon discovery along with actions taken. The site should actively pursue options for returning the study intervention to labeled storage conditions, as soon as possible. Once an excursion is identified, the study intervention must be quarantined and not used until Pfizer provides permission to use the study intervention. Specific details regarding the excursion definition and information to report for each excursion will be provided to the site in the IPM.
5. Any storage conditions stated in the SRSD will be superseded by the storage conditions stated on the label. See the IPM for storage conditions of the study intervention.
6. Study interventions should be stored in their original containers.
7. The investigator, institution, head of the medical institution (where applicable), or authorized site staff is responsible for study intervention accountability, reconciliation, and record maintenance (ie, receipt, reconciliation, and final disposition records), such as the IPAL or sponsor-approved equivalent. All study interventions will be accounted for using a study intervention accountability form/record.
8. Further guidance and information for the final disposition of unused study interventions are provided in the IPM. All destruction must be adequately documented. If destruction is authorized to take place at the investigator site, the investigator must ensure that the materials are destroyed in compliance with applicable environmental regulations, institutional policy, and any special instructions provided by Pfizer.

Upon identification of a product complaint, notify the sponsor within 1 business day of discovery as described in the IPM.

#### **6.2.1. Preparation and Dispensing**

Study intervention will be prepared by qualified unblinded site personnel according to the IPM or package insert, and the study intervention administered in such a way to ensure the participants remain blinded.

Study intervention should be prepared and dispensed by an appropriately qualified and experienced member of the study staff (eg, physician, nurse, physician's assistant, nurse practitioner, pharmacy assistant/technician, or pharmacist) as allowed by local, state, and institutional guidance. A second staff member will verify the dispensing.

#### **6.3. Assignment to Study Intervention**

Allocation (randomization) of participants to vaccine groups will proceed through the use of an IRT system. The site personnel (study coordinator or specified designee) will be required to enter or select information including, but not limited to, the user's ID and password, the protocol number, and the participant number. The site personnel will then be provided with a randomization number. The IRT system will provide a confirmation report containing the participant number, randomization number, and study intervention allocation assigned. This report will be provided to blinded or unblinded site staff as appropriate on the

role/permission the user is granted and must be stored in the site's blinded or unblinded files as appropriate.

Study intervention will be dispensed at the study visits summarized in the [SoA](#).

The study-specific IRT reference manual and IPM will provide the contact information and further details on the use of the IRT system.

#### **6.4. Blinding**

See [Section 10.11.6.4](#) for Substudy A blinding arrangements.

See [Section 10.12.6.4](#) for Substudy B blinding arrangements.

See [Section 10.13.6.4](#) for Substudy C blinding arrangements.

#### **6.5. Study Intervention Compliance**

When participants are dosed at the site, they will receive study intervention directly from the investigator or designee, under medical supervision. The date and time of each dose administered in the clinic will be recorded in the source documents and recorded in the CRF. The dose of study intervention and study participant identification will be confirmed at the time of dosing by a member of the study site staff other than the person administering the study intervention.

#### **6.6. Dose Modification**

Not applicable.

#### **6.7. Continued Access to Study Intervention After the End of the Study**

No study intervention will be provided to participants at the end of their study participation.

#### **6.8. Treatment of Overdose**

For this study, any dose greater than 1 dose of study intervention within a 24-hour time period will be considered an overdose.

Pfizer does not recommend specific treatment for an overdose.

In the event of an overdose, the investigator should:

1. Contact the study medical monitor within 24 hours.
2. Closely monitor the participant for any AEs/SAEs as medically appropriate and follow up until resolution, stabilization, the event is otherwise explained, or the participant is lost to follow-up (as defined in [Section 7.3](#)).

3. Document the quantity of the excess dose as well as the duration of the overdose in the CRF.
4. Overdose is reportable to Pfizer Safety only when associated with an SAE.

See [Section 8.4.10](#) for vaccination error reporting requirements, which include administration of an incorrect dosage.

## **6.9. Prior and Concomitant Therapy**

See [Section 10.11.6.9](#) for Substudy A prior and concomitant therapy.

See [Section 10.12.6.9](#) for Substudy B prior and concomitant therapy.

See [Section 10.13.6.9](#) for Substudy C prior and concomitant therapy.

## **7. DISCONTINUATION OF STUDY INTERVENTION AND PARTICIPANT DISCONTINUATION/WITHDRAWAL**

### **7.1. Discontinuation of Study Intervention**

Since this is a single-dose study, this section is not applicable.

#### **7.1.1. Pregnancy**

In the case of a positive confirmed pregnancy, the participant will not be administered the study intervention and will be withdrawn from the study.

### **7.2. Participant Discontinuation/Withdrawal From the Study**

A participant may withdraw from the study at any time at their own request. Reasons for discontinuation from the study include the following:

- Refused further study procedures;
- Lost to follow-up;
- Death;
- Study terminated by sponsor;
- AEs;
- Reactogenicity;
- Participant request;
- Investigator request;
- Protocol deviation

Participants may remain in the study for safety evaluation and be contacted by telephone 6 months after their last study vaccination to record SAEs.

If a participant does not return for a scheduled visit, every effort should be made to contact the participant. All attempts to contact the participant and information received during contact attempts must be documented in the participant's source document. In any circumstance, every effort should be made to document participant outcome, if possible.

The investigator or their designee should capture the reason for withdrawal in the CRF for all participants.

If a participant withdraws from the study, they may request destruction of any remaining samples taken and not tested, and the investigator must document any such requests in the site study records and notify the sponsor accordingly.

If the participant withdraws from the study and also withdraws consent (see Section 7.2.1) for disclosure of future information, no further evaluations will be performed and no additional data will be collected. The sponsor may retain and continue to use any data collected before such withdrawal of consent.

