#### **8.4.1. Time Period and Frequency for Collecting AE and SAE Information**

The time period for actively eliciting and collecting AEs and SAEs (“active collection period”) for each participant begins from the time the participant provides informed consent, which is obtained before the participant’s participation in the study (ie, before undergoing any study-related procedure and/or receiving study intervention), through and including Visit 102 in Substudy A, Visit 202 in Substudy B, and Visit 303 in Substudy C.

Additionally, MAEs, NDCMCs, and SAEs will be collected from the time the participant provides informed consent to Visit 103 in Substudy A, Visit 203 in Substudy B, and Visit 304 in Substudy C (approximately 6 months after vaccination). In addition, AEs occurring up to 48 hours after blood draws must be recorded on the CRF.

Follow-up by the investigator continues throughout the active collection period and until the AE or SAE or its sequelae resolve or stabilize at a level acceptable to the investigator.

When a clinically important AE remains ongoing at the end of the active collection period, follow-up by the investigator continues until the AE or SAE or its sequelae resolve or stabilize at a level acceptable to the investigator and Pfizer concurs with that assessment.

For participants who are screen failures, the active collection period ends when screen failure status is determined.

If the participant withdraws from the study and also withdraws consent for the collection of future information, the active collection period ends when consent is withdrawn.

If a participant permanently discontinues or temporarily discontinues from the study because of an AE or SAE, the AE or SAE must be recorded on the CRF and the SAE reported via PSSA.

Investigators are not obligated to actively seek information on AEs or SAEs after the participant has concluded study participation. However, if the investigator learns of any SAE, including a death, at any time after a participant has concluded study participation, and they consider the event to be reasonably related to the study intervention, the investigator must promptly report the SAE to Pfizer via PSSA.

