#### **10.3.6. Medically Attended AE**

An MAE is defined as a nonserious AE that results in an evaluation at a medical facility.

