2.2.1. Primary Estimand(s)

The primary estimands for the primary objective (safety) will use the treatment policy strategy and estimate the safety event rate (reactogenicity, AEs/SAEs/MAEs/NDCMCs) regardless of whether an intercurrent event occurs.

- The reactogenicity estimands (local reactions and systemic events) have the following 5 attributes:
 - Treatment condition:** Vaccination with 3 different formulations of tIRV (tIRV1, tIRV2, and tIRV3), QIV1 (CCI), and qIRV1 as defined in Section 2.3.
 - Population:** Participants 18 through 64 years of age who receive the study intervention.
 - Variables:** Local reactions and systemic events from the e-diary up to 7 days following vaccination.
 - Intercurrent events:** All data after an intercurrent event (receiving prohibited vaccine or concomitant therapy, receiving the vaccine not as randomized, use of rescue medication, missing e-diary entries on certain days, study discontinuation), if collected, will be included.
 - Population-level summary:** The rates of reporting each prompted reactogenicity item, and the associated 2-sided 95% CIs, by study intervention group (in the tIRV1, tIRV2, tIRV3, QIV1 and qIRV1 vaccine groups, separately).
- The AE, SAE, MAE and NDCMC estimands have the following 5 attributes:
 - Treatment condition:** Vaccination with 3 different formulations of tIRV (tIRV1, tIRV2, and tIRV3), QIV1 (CCI), and qIRV1 as defined in Section 2.3.
 - Population:** Participants 18 through 64 years of age who receive the study intervention.

- **Variables:**
 - AEs reported through 4 weeks after vaccination.
 - SAEs reported through 6 months after vaccination.
 - MAEs reported through 6 months after vaccination.
 - NDCMCs reported through 6 months after vaccination.
- **Intercurrent events:** All data after an intercurrent event (receiving prohibited vaccine or concomitant therapy, receiving the vaccine not as randomized, use of rescue medication, study discontinuation), if collected, will be included.
- **Population-level summary:** The rates of AEs, SAEs, MAEs and NDCMCs, and the associated 2-sided 95% CIs, by study intervention group (in the tIRV1, tIRV2, tIRV3, QIV1 and qIRV1 vaccine groups, separately).

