6.1.2. AEs, SAEs, MAEs, and NDCMCs

6.1.2.1. Main Analysis

- Estimand strategy: Treatment policy ([Section 2.2.1](#)).
- Analysis set: Safety population ([Section 4](#)).
- Analysis methodology: 95% CI of the proportion of participants reporting such events, using the Clopper-Pearson method ([Section 5.2.1](#)).
- Analysis timing: Day 1 through 4 weeks after vaccination for AEs; Day 1 through 6 months after vaccination for SAEs, MAEs, and NDCMCs.
- Intercurrent events and missing data: All data collected are included. Missing AE dates will be imputed as described in Pfizer's Vaccine Statistics Rulebook.

Reporting results:

- The number of participants with AEs through 4 weeks after vaccination (n), the proportion (%), and the associated 2-sided Clopper-Pearson 95% CIs will be presented for each study intervention group.
- The number of participants with SAEs, MAEs, and NDCMCs through 6 months after vaccination (n), the proportion (%), and the associated 2-sided Clopper-Pearson 95% CIs will be presented for each study intervention group.
- Descriptive statistics, including the proportion (%), the numerator (n) and the denominator used in the proportion calculation, and the 95% CIs for the percentage using the Clopper-Pearson method, will be presented for each SOC and each PT within each SOC for each study intervention group.

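### Protocol 7.2 limits the 6-month call to withdrawn participants to SAEs, in conflict with 8.4.1; if sites follow 7.2, some primary safety proportions would be understated

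*Protocol*

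**What the plan says.** **Contact after withdrawal.** Protocol section 7.2 states: "Participants may remain in the study for safety evaluation and be contacted by telephone 6 months after their last study vaccination to record SAEs". No other section describes a contact made specifically with people who have left the study.

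**Collection period.** Protocol section 8.4.1 is wider. It runs AE collection for each participant through Visit 102, 202 or 303 (about 4 weeks), and adds that "MAEs, NDCMCs, and SAEs will be collected from the time the participant provides informed consent to Visit 103 in Substudy A", with Visits 203 and 304 as the counterparts in Substudies B and C. For a participant who withdraws, it closes the collection period only when consent for future information is withdrawn too.

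**Primary endpoints.** SAP section 2.2.1 (Substudy A; B and C match) lists among the primary variables "AEs reported through 4 weeks after vaccination", "MAEs reported through 6 months after vaccination" and "NDCMCs reported through 6 months after vaccination", alongside SAEs to 6 months. Protocol section 10.3.6 adds: "An MAE is defined as a nonserious AE that results in an evaluation at a medical facility".

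**Analysis.** The safety population is everyone vaccinated (SAP section 4). The strategy is treatment policy, with data after intercurrent events retained where they exist; the sentence ends "use of rescue medication, study discontinuation), if collected, will be included". SAP section 6.1.2.1 then reports, by group, "The number of participants with SAEs, MAEs, and NDCMCs through 6 months after vaccination (n), the proportion" and its exact interval. Only missing AE dates are imputed.

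**The concern.** An MAE is nonserious by definition, so a call that asks only about SAEs cannot record one. The same holds for a nonserious NDCMC or a nonserious AESI such as confirmed influenza. Someone who leaves before the 4-week visit also loses part of the 4-week AE window, and the only contact that 7.2 offers comes at 6 months.

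The analysis has no rule for this. For reactogenicity, SAP section 6.1.1.1 removes participants who have no data. For AEs, MAEs and NDCMCs, section 6.1.2.1 keeps everyone vaccinated in the denominator, so an event that nobody asked about counts as no event. The error can only lower a safety rate, and it would fall on primary endpoints in all three substudies. The treatment-policy estimand would also be incompletely delivered for people who had agreed to be followed.

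**Working it through.** **Step 1. Reproduce the plan's own figures.** The sample-size tables use P(at least 1 event) = 1 − (1 − p)^n.

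- n = 90 (Tables 6 and 8), p = 0.5, 1, 2, 5, 7%: 36.3, 59.5, 83.8, 99.0, 99.9%. All match.
- n = 30 (Table 11), same rates: 14.0, 26.0, 45.5, 78.5, 88.7%. All match.

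These figures treat every vaccinated participant as fully observed.

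**Step 2. Set the two sections side by side for a participant who withdraws and still consents to contact.**

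| Event | Under 7.2 | Under 8.4.1 |
|---|---|---|
| SAE to 6 months | asked | collected |
| MAE to 6 months | not asked | collected |
| Nonserious NDCMC to 6 months | not asked | collected |
| AE to 4 weeks, left before Visit 102/202/303 | not asked | collected |
| AE to 4 weeks, left after that visit | already complete | already complete |

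**Step 3. Size, if 7.2 is followed.** Let p be the true proportion with the event, w the share of the group who withdraw into SAE-only follow-up, and m the share of those participants' events that goes unrecorded (below 1 because events recorded before withdrawal are kept). With equal event risk in leavers and stayers:

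- observed proportion = p(1 − w·m)
- relative shortfall = w·m
- participants missed = n·p·w·m

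The documents give no withdrawal rate and no MAE or NDCMC rate. I assume w = 2% to 10% and m = 0.5 to 1. The relative shortfall then runs from 0.02 × 0.5 = 1% to 0.10 × 1 = 10%.

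| True p | Observed p | Missed per 90 | Missed per 30 |
|---|---|---|---|
| 10% | 9.0% to 9.9% | 0.09 to 0.9 | 0.03 to 0.3 |
| 20% | 18.0% to 19.8% | 0.18 to 1.8 | 0.06 to 0.6 |

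At a true rate of 2%, the chance of seeing at least one event falls from 83.8% to between 80.5% and 83.5% (n = 90), and from 45.5% to between 42.0% and 45.1% (n = 30).

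For the 4-week AE endpoint, w counts only those who leave before the 4-week visit, so it cannot exceed the w for the 6-month endpoints.

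**Step 4. Scale against sampling error.** The Clopper-Pearson 95% interval is 4.7% to 18.1% for 9/90 and 3.9% to 16.8% for 8/90. One missed participant moves the interval by much less than its width.

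**Step 5. Sensitivity to the equal-risk assumption.** If leavers had r times the risk of stayers and all their events were missed (m = 1), the relative shortfall is rw/(1 − w + rw). With w = 5% and r = 2 it is 0.10/1.05 = 9.5%; with w = 10% and r = 3 it is 0.30/1.20 = 25%. Nothing in the documents gives r, so this is an outer bound on an assumption.

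**Step 6. If 8.4.1 is followed,** m = 0 and the shortfall from this source is zero.

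**The case against.** The strongest reply is that 8.4.1 governs. It sets collection for every participant and ends it for someone who withdraws only on withdrawal of consent, so a person who accepts follow-up is still covered. Section 7.2 is permissive, does not say that other events are to be left out, and itself stops data collection only when consent is withdrawn as well. This stands, and it is why the defect is a conflict between sections rather than a settled SAE-only rule. It does not remove the defect. Section 8.4.1 ends collection at visits that a withdrawn participant does not attend and names no contact to replace them; 7.2 does name one, and its stated purpose is SAEs. Section 7.2.1 does not fill the gap: its continued follow-up is for people who stop receiving study intervention, and 7.1 says that discontinuation of intervention does not apply in a single-dose study.

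Three stronger readings are tempting, and the documents do not support them.

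- **That the rates are undercounted.** This depends on which section sites follow, and on withdrawals and later events whose frequency is not given.
- **That the bias is greatest in the more reactogenic groups.** AEs and reactogenicity are listed reasons for leaving, but the AE behind a discontinuation must go on the CRF (8.4.1), as must e-diary events behind a withdrawal (8.3.4). What could be lost is a later nonserious event, and nothing shows that this differs by group.
- **That myocarditis or pericarditis would go undetected.** Participants are told at vaccination to contact the site about chest pain, shortness of breath or palpitations, and anyone reporting such symptoms within 28 days is to be evaluated. The 6-month call was never the route for a 28-day event.

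It is also fair to say that the SAP discloses the limit by conditioning on data having been collected, and that section 6.6.2.1 tabulates withdrawals with reasons by group. That shows how many left, but not how many of them have incomplete safety follow-up.

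**Conclusion.** The point holds as an inconsistency with a conditional consequence. Sections 7.2 and 8.4.1 disagree on which primary safety events are sought from people who withdraw but still consent to contact. If 7.2 is followed, the MAE and NDCMC proportions, and the AE proportion for those who leave before the 4-week visit, would be understated. The relative size is about 1% to 10% under assumed withdrawal of 2% to 10%, half to all events missed, and equal event risk. That is under one participant per group of 90 at a true rate of 10%, and zero if 8.4.1 is followed. The study is descriptive and tests no hypothesis, so no formal conclusion turns on it. It is still worth correcting, because the direction is downward on primary safety endpoints and the correction is cheap.

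**What to change.** 1. In protocol section 7.2, widen the purpose of the 6-month call from SAEs to SAEs, MAEs, NDCMCs and AESIs since last contact, so that it agrees with 8.4.1.
2. For participants who leave before Visit 102, 202 or 303 and still consent, also seek AEs through 4 weeks after vaccination, by a telephone contact at 4 weeks where they agree.
3. In each SAP, report by group the number with incomplete 4-week and 6-month safety follow-up beside the proportions in section 6.1.2.1.

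The cost is a few more questions on a call already provided for, a 4-week call for early leavers who agree, and one extra tabulation. The downside is that recall of nonserious events at 6 months is imperfect, so the wider call would reduce the shortfall rather than remove it.
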